4.4.2 Prohibited and Cautionary Therapy

Use of the following concomitant therapies is prohibited as described below:

- Concomitant therapy intended for the treatment of cancer (including, but not limited to, chemotherapy, hormonal therapy, immunotherapy, radiotherapy, and herbal therapy), whether health authority–approved or experimental, is prohibited for various time periods prior to starting study treatment, depending on the agent (see Section 4.1.2), and during study treatment, until disease progression is documented and the patient has discontinued study treatment, with the exception of palliative radiotherapy and local therapy under certain circumstances (see Section 4.4.1 for details).
- Investigational therapy is prohibited within 21 days prior to initiation of study treatment and during study treatment.
- Live, attenuated vaccines (e.g., FluMist[®]) are prohibited within 4 weeks prior to initiation of study treatment, during atezolizumab and/or venetoclax treatment, and for 5 months after the final dose of atezolizumab and at least 28 days after the final dose of venetoclax.

- Systemic immunostimulatory agents (including, but not limited to, interferons and IL-2) are prohibited within 4 weeks or 5 drug-elimination half-lives (whichever is longer) prior to initiation of study treatment and during study treatment because these agents could potentially increase the risk for autoimmune conditions when given in combination with atezolizumab.
- Systemic immunosuppressive medications (including, but not limited to, cyclophosphamide, azathioprine, methotrexate, and thalidomide) are prohibited during study treatment because these agents could potentially alter the efficacy and safety of atezolizumab.
- Systemic corticosteroids and TNF-α inhibitors may attenuate potential beneficial immunologic effects of treatment with atezolizumab. Therefore, in situations in which systemic corticosteroids or TNF-α inhibitors would be routinely administered, alternatives, including antihistamines, should be considered. If the alternatives are not feasible, systemic corticosteroids and TNF-α inhibitors may be administered at the discretion of the investigator. Systemic corticosteroids are recommended, at the discretion of the investigator, for the treatment of specific adverse events when associated with atezolizumab therapy (refer to Appendix 13 for details).

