In addition, the investigator should contact the Medical Monitor if questions arise regarding medications not listed. A decision may be made to allow the use of prohibited medications on a case by case basis, following discussion with the Medical Monitor and assessment of the benefit–risk ratio.

Patients who require the use of any therapies when they are prohibited (unless an allowance is made after consultation with the Medical Monitor) will be discontinued from study treatment and followed for safety outcomes for 4 weeks after the last dose of study treatment or until initiation of another subsequent anti-cancer therapy, whichever comes first.

Refer to the local prescribing information for information on potential drug interactions between etoposide or carboplatin and concomitant medications.

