For patients with previously untreated CNS metastases, a brain MRI scan with contrast is required at screening and is the preferred modality for all subsequent scheduled follow-up tumor assessments. Note: CT scan with contrast may be acceptable for all subsequent scheduled follow-up tumor assessments if the following criteria are met: (1) Both brain MRI and CT scan with contrast must be performed at screening to assess untreated CNS disease, and (2) The CT scan with contrast can be used to reliably evaluate lesions identified on the screening MRI with contrast. If CT scan with contrast cannot be used to reliably evaluate lesions identified on the screening MRI with contrast, then MRI scan with contrast must be used at all subsequent scheduled follow-up tumor assessments. The same modality must be used at every tumor assessment.

Untreated CNS disease must be recorded in the Tumor Assessment eCRF per RECIST 1.1 at screening as well as at subsequent scheduled follow-up tumor assessments.

Patients will undergo tumor assessments at baseline and at every 6 weeks (\pm 7 days) for 48 weeks following Day 1 of Cycle 1 regardless of treatment delays. After the completion of the Week 48 tumor assessment, tumor assessment will be required every 9 weeks (\pm 7 days) regardless of treatment delays, until radiographic disease progression per RECIST v1.1 (or loss of clinical benefit for patients who continue study treatment after disease progression per RECIST v1.1), withdrawal of consent, death, or study termination by the Sponsor, whichever occurs first (see Section 3.1.6). At the investigator's discretion, scans may be performed at any time if progressive disease or loss of clinical benefit is suspected. *Patients who continue treatment beyond radiographic disease progression per RECIST v1.1 will undergo tumor assessments at the frequency described above, which is every 6 weeks (\pm7 days) for 48 weeks following Cycle 1, Day 1 and then every 9 weeks* (\pm 7 days) thereafter, until study treatment is discontinued.

Response will be assessed by the investigator on the imaging modalities detailed above, using RECIST v1.1 (see Appendix 5). The investigator's assessment of overall tumor response at all timepoints should only be based on RECIST v1.1. Assessments should be performed by the same evaluator if possible to ensure internal consistency across visits. Results must be reviewed by the investigator before dosing at the next cycle.

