Study treatment may be continued as long as patients are experiencing clinical benefit as assessed by the investigator in the absence of unacceptable toxicity or symptomatic deterioration attributed to disease progression after an integrated assessment of radiographic data, biopsy results (if available), and clinical status. Patients who meet criteria for disease progression per RECIST v1.1 will be permitted to continue study treatment if they meet all of the criteria specified in Section 3.1.6.

Patients who discontinue treatment for reasons other than radiographic disease progression per RECIST v1.1 (e.g., toxicity, symptomatic deterioration) will continue scheduled tumor assessments at the frequency described above until radiographic disease progression per RECIST v1.1, withdrawal of consent, death, or study termination by Sponsor, whichever occurs first. Patients who start a new anti-cancer therapy in the absence of radiographic disease progression per RECIST v1.1 will continue tumor assessments at the frequency described above until radiographic disease progression per RECIST v1.1 will continue tumor assessments at the frequency described above until radiographic disease progression per RECIST v1.1, withdrawal of consent, death, or study termination by the Sponsor, whichever occurs first.

Investigator assessment of overall tumor response at all timepoints will be only based on RECIST v1.1.

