Patients will return to the clinic for a treatment discontinuation visit \leq 30 days after the final dose of study treatment (see Appendix 1). The visit at which response assessment shows progressive disease may be used as the treatment discontinuation visit. Patients who discontinue study treatment for any reason other than progressive disease or loss of clinical benefit will continue to undergo tumor response assessments and PRO assessments as outlined in the schedule of activities (see Appendix 1 and Appendix 2).

After treatment discontinuation, information on survival follow-up and new anti-cancer therapy will be collected via telephone calls, patient medical records, and/or clinic visits approximately every 3 months until death (unless the patient withdraws consent or the Sponsor terminates the study) (see Appendix 1 and Appendix 2). Information on subsequent anti-cancer therapies will include systemic therapies (e.g., chemotherapy, targeted therapy, hormonal therapy, or CIT), surgery (e.g., resection of metastatic disease), and radiation procedures (e.g., radiotherapy to a tumor lesion).

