5.3.1 Adverse Event Reporting Period

Investigators will seek information on adverse events at each patient contact. All adverse events, whether reported by the patient or noted by study personnel, will be recorded in the patient's medical record and on the Adverse Event eCRF.

After informed consent has been obtained but prior to initiation of study treatment, only serious adverse events caused by a protocol-mandated intervention (e.g., invasive procedures such as biopsies, discontinuation of medications) should be reported (see Section 5.4.2 for instructions for reporting serious adverse events).

After initiation of study treatment, all adverse events will be reported until 30 days after the last dose of study drug or until initiation of new systemic anti-cancer therapy, whichever occurs first, and serious adverse events and adverse events of special interest will continue to be reported until 90 days after the final dose of study treatment or until initiation of new systemic anti-cancer therapy, whichever occurs first.

Instructions for reporting adverse events that occur after the adverse event reporting period are provided in Section 5.6.

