6.5.2.2 Progression-Free Survival

PFS after enrollment is defined as the time from enrollment to the first occurrence of disease progression or relapse or death from any cause (whichever occurs first), as determined by the investigator according to RECIST v1.1 criteria. Data for patients without the occurrence of disease progression or death as of the clinical data cutoff date will be censored at the time of last tumor assessment (or the time of enrollment plus 1 day if no tumor assessment was performed after the baseline visit).

The Kaplan-Meier approach will be used to estimate median PFS. The Kaplan-Meier curve of time to PFS will be provided.

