- If the patient discontinued study treatment for any reason other than radiographic disease progression per RECIST v1.1 (e.g., toxicity, symptomatic deterioration), tumor assessments will continue at the same frequency as would have been followed if the patient had remained on study treatment (i.e., every 6 weeks [± 7 days] for 48 weeks following Cycle 1, Day 1 and then every 9 weeks [± 7 days] thereafter) until radiographic disease progression per RECIST v1.1, withdrawal of consent, death, or study termination by the Sponsor, whichever occurs first, even if the patient starts another anti-cancer therapy after study treatment discontinuation, unless consent is withdrawn.
- Optional tumor biopsy at radiographic disease progression, if clinically feasible, preferably within 40 days of radiographic progression or prior to start of the next anti-cancer therapy, whichever occurs first.
- * All serious adverse events and adverse events of special interest, regardless of relationship to study drug, will be reported until 90 days after the last dose of study drug or initiation of new systemic anti-cancer therapy after the last dose of study drug, whichever occurs first. All other adverse events, regardless of relationship to study drug, will be reported until 30 days after the last dose of study drug or initiation of new systemic anti-cancer therapy after the last dose of study drug or initiation of new systemic anti-cancer therapy after the last dose of study drug or initiation of new systemic anti-cancer therapy after the last dose of study drug or initiation. In addition, the Sponsor should be notified if the investigator becomes aware of any serious adverse event or adverse event of special interest that is believed to be related to prior exposure to study treatment. These events should be reported through use of the Adverse Event eCRF.
- ^y From 7 days before screening until the treatment discontinuation visit. All such medications should be reported to the investigator and recorded on the Concomitant Medications eCRF.

Venetoclax—F. Hoffmann-La Roche Ltd Page 159 of 214 Protocol GO41864, Version 2

[•] Thyroid function testing (TSH, free T3, free T4) collected on Day 1 of Cycles 1, 4, 8, and 12, and every fourth cycle thereafter.

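### Two sentences on follow-up after discontinuation, in Sections 4.6.1 and 4.4.2, contradict the rules stated elsewhere; read literally, the first would shift PFS and DOR upward and the second would shorten SAE and AESI collection

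*Combined protocol and SAP*

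**What the plan says.** **Tumor follow-up.** Section 4.6.1 states: "Patients who discontinue study treatment for any reason other than progressive disease or loss of clinical benefit will continue to undergo tumor response assessments". The sentence goes on to refer to Appendices 1 and 2 for the schedule.

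Section 4.5.5 states: "Patients who discontinue treatment for reasons other than radiographic disease progression per RECIST v1.1 (e.g., toxicity, symptomatic deterioration) will continue scheduled tumor assessments", and these run until RECIST v1.1 progression, withdrawal of consent, death or study termination. The footnote on post-discontinuation scans in Appendix 1, repeated in Appendix 2, agrees: "If the patient discontinued study treatment for any reason other than radiographic disease progression per RECIST v1.1 (e.g., toxicity, symptomatic deterioration), tumor assessments will continue". Section 4.5.5 does let loss of clinical benefit end scanning, but only in one group: "or loss of clinical benefit for patients who continue study treatment after disease progression per RECIST v1.1".

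**PFS.** Section 6.5.2.2 counts RECIST progression, relapse or death. A patient with none of these by the cutoff "will be censored at the time of last tumor assessment". Section 6.5.2.1 treats DOR in the same way.

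**Safety follow-up.** Under Section 4.4.2, patients who need a prohibited therapy, with no allowance from the Medical Monitor, come off treatment and are "followed for safety outcomes for 4 weeks after the last dose of study treatment or until initiation of another subsequent anti-cancer therapy", whichever is first. Section 5.3.1 sets 30 days for all adverse events and, beyond that, "serious adverse events and adverse events of special interest will continue to be reported until 90 days after the final dose of study treatment". Either period ends early if new systemic anti-cancer therapy starts. Sections 5.4.2.2 and 5.6 and the appendix footnotes repeat the 90 days, and the footnotes repeat the 30. None makes an exception for the prohibited-therapy group.

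**The concern.** Section 4.6.1 lists symptomatic deterioration as a mandatory reason to stop treatment, separate from radiographic progression, and Section 3.3.1 describes fast clinical deterioration as typical of this population. Stopping treatment before RECIST progression is therefore a realistic path. Symptomatic deterioration is not itself a PFS event: Appendix 5 calls it a reason for stopping therapy, not an objective response. Whether such a patient is scanned again decides whether and when PFS records the progression.

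The study is non-randomized, so no control arm offsets a one-sided shift in the expansion cohort. The confidence interval planned for the 6-month rate covers sampling error only. Scans that were not done cannot be recovered at analysis.

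On safety, the stake is whether new SAEs and AESIs are actively collected for as long in the prohibited-therapy subgroup as in everyone else.

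**Working it through.** **1. Who is scanned after stopping treatment**

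| Reason for stopping | 4.6.1, read literally | 4.5.5 and appendix footnotes |
|---|---|---|
| RECIST progression | no further scans required | no further scans required |
| Toxicity | scans continue | scans continue to RECIST progression |
| Clinical deterioration before RECIST progression | falls under loss of clinical benefit: no further scans required | scans continue to RECIST progression |

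The rules differ in the last row only. The restriction that would reconcile them (patients already past RECIST progression) is written in 4.5.5 but not in 4.6.1.

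**2. Direction of the effect.** Suppose scans stop at deterioration and progression follows unseen.
- If the patient dies before the cutoff, the event is dated at death, later than the progression.
- If the patient is alive at the cutoff, the time is censored at the last scan, just before the progression and because of it.

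Both move PFS upward. DOR moves the same way in responders.

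**3. Illustrative size for the 6-month PFS rate.** The documents do not say how many patients would be affected, so the following are assumptions, not trial figures:
- Progression times are exponential with median 5.2 months, and post-progression time is exponential and set so that median OS is 12.3 months. Both medians are for atezolizumab plus chemotherapy in Section 1.2.
- Scans are every 6 weeks to week 48, then every 9 weeks (Section 4.5.5). Cutoff is at 24 months.
- A fraction f of patients stops being scanned just before RECIST progression.

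A Kaplan-Meier simulation of 400,000 patients gives:

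| f | Patients of 20 | Scans continued | 4.6.1 literal, deaths counted | 4.6.1 literal, all affected censored at last scan |
|---|---|---|---|---|
| 10% | 2 | 47.7% | 50.9% (+3.2) | 50.8% (+3.1) |
| 20% | 4 | 47.7% | 54.0% (+6.3) | 54.3% (+6.6) |
| 30% | 6 | 47.7% | 57.2% (+9.5) | 58.0% (+10.3) |

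Hand check. The mean time to progression is a = 5.2/ln 2 = 7.50 months, and the fitted mean post-progression time is b = 7.18 months.
- With scans continued, the last scan before month 6 is at 4 × 42/30.44 = 5.52 months. The rate is about exp(−5.52/7.50) = 0.479, slightly lowered by deaths between scans, which agrees with 0.477.
- An affected patient is event-free at 6 months if alive: (a·exp(−6/a) − b·exp(−6/b))/(a − b) = 0.80.
- The shift is f × (0.80 − 0.477), or about 0.33f: 3.3, 6.5 and 9.8 points.

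Deteriorated patients may die sooner than the average patient who progresses. Halving b to 3.59 months for them alone gives 0.69 in place of 0.80, and shifts of 0.212f: 2.1, 4.2 and 6.4 points.

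For scale, the 90% half-width at a 50% rate with 20 patients is 1.645 × √(0.25/20) = 0.184, about 18 points.

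**4. Safety windows.** Four weeks is 28 days.
- SAEs and AESIs: 90 − 28 = 62 days, or 62/90 = 69% of the window.
- Other AEs: 30 − 28 = 2 days.
- The stopping triggers also differ: any subsequent anti-cancer therapy in 4.4.2, new systemic anti-cancer therapy in 5.3.1.

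**The case against.** The strongest reply on scans is that 4.6.1 never orders them to stop and itself points to Appendices 1 and 2, which require them. Appendix 5 asks for every effort to document objective progression after discontinuation, and Section 5.3.5.10 is similar. Loss of clinical benefit may also have been meant as in 4.5.5, for patients treated past RECIST progression, who already have their PFS event. This stands to a degree: a reader might infer that PFS is biased as a matter of fact, and the documents do not support that, because the bias arises only where a site follows the one sentence over several others. The reply does not remove the conflict. The sentence states who continues before it says where the schedule is found, and it lacks the restriction that 4.5.5 carries.

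On safety, a reader might infer that patients with the worst immune toxicity get the shortest follow-up, because systemic immunosuppressants "are prohibited during study treatment because these agents could potentially alter the efficacy and safety of atezolizumab" while Appendix 13 suggests adding one for severe events. The documents do not support this. The 4-week rule is triggered by any prohibited drug, for example a strong CYP3A inducer, and only without a Medical Monitor allowance. Section 4.4.2 leaves corticosteroids and TNF-α inhibitors to the investigator's discretion. The Appendix 13 entries that add an immunosuppressive agent already direct contact with the Medical Monitor. Section 5.5.1 also follows ongoing events until resolved or stable, and Section 5.6 still takes in late related SAEs that the investigator learns of.

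On size, a reader might count each affected patient as 5 points (1/20). That requires every one of them to progress before month 6 and outlive it; under the assumptions above an affected patient is worth about 0.33 × 5 = 1.6 points. Subtracting the cited medians (12.3 − 5.2 = 7.1 months) does not measure survival after deterioration either, and those medians run from first-line induction, so they do not describe a maintenance-only expansion.

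**Conclusion.** Both contradictions are in the current text and should be reconciled; their consequences are conditional.

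If 4.6.1 is applied literally, PFS, 6-month PFS and DOR shift upward. The illustration gives about 3, 6 and 10 points on the 6-month rate for 10%, 20% and 30% affected, and less if deteriorated patients die sooner than assumed. The affected fraction is unknown, and these shifts are smaller than the sampling uncertainty at 20 patients. The endpoints concerned are secondary and descriptive, deaths remain PFS events, and ORR and OS are largely unaffected.

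If 4.4.2 is applied literally, systematic collection of new SAEs and AESIs is lost on days 29 to 90, in the prohibited-therapy subgroup only, whose size is not stated. It does not follow that late serious toxicity goes unseen in general. No sample size or precision figure changes.

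**What to change.** In Section 4.6.1, make radiographic disease progression per RECIST v1.1 the only reason for stopping treatment that ends tumor assessments, in line with 4.5.5 and the schedule footnotes. In Section 4.4.2, reconcile the 4-week sentence, including its anti-cancer-therapy trigger, with the reporting periods in 5.3.1.

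The cost is two sentences in an amendment. The scans and the reporting are already required elsewhere in the protocol. The downside is a few more scans in patients who have deteriorated, some of whom will decline them.

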4.6.2 Patient Discontinuation from the Study

Patients have the right to voluntarily withdraw from the study at any time for any reason. In addition, the investigator has the right to withdraw a patient from the study at any time.

Reasons for patient discontinuation from the study may include, but are not limited to, the following:

- Patient withdrawal of consent
- Study termination or site closure
- Loss to follow-up
- Patient non-compliance, defined as failure to comply with protocol requirements as determined by the investigator or Sponsor

Every effort should be made to obtain a reason for patient discontinuation from the study. The primary reason for discontinuation from the study should be documented on the appropriate eCRF. If a patient requests to be withdrawn from the study, this request must be documented in the source documents and signed by the investigator. Patients who withdraw from the study will not be replaced.

If a patient withdraws from the study, the study staff may use a public information source (e.g., county records) to obtain information about survival status.

4.6.3 Study Discontinuation

The Sponsor has the right to terminate this study at any time. Reasons for terminating the study may include, but are not limited to, the following:

- The incidence or severity of adverse events in this or other studies indicates a potential health hazard to patients
- Patient enrollment is unsatisfactory

The Sponsor will notify the investigator if the Sponsor decides to discontinue the study.

4.6.4 Site Discontinuation

The Sponsor has the right to close a site at any time. Reasons for closing a site may include, but are not limited to, the following:

- Excessively slow recruitment
- Poor protocol adherence
- Inaccurate or incomplete data recording
- Non-compliance with the International Council for Harmonisation (ICH) guideline for Good Clinical Practice
- No study activity (i.e., all patients have completed the study and all obligations have been fulfilled)

5. ASSESSMENT OF SAFETY

